Patients diagnosed with Stage IIB/C disease have thicker melanomas (> 2.0 mm). These patients have an unmet clinical need as there is no clear safe and effective systemic adjuvant therapy to prevent disease relapse once the primary tumor has been completely resected, which is the current standard of care for these patients. Approximately, 15% to 20% of patients diagnosed with Stage IIB and 30% of patients diagnosed with Stage IIC melanoma will have a relapse of their melanoma at 24 months.⁷ Within 5 years of surgical resection, approximately 25% of patients with Stage IIB disease and 40% of patients with Stage IIC disease will have a relapse of their disease.⁸ A SEER Registry review conducted by Landow et al. (2016) revealed that 7.4% (95% CI: 7.2-7.7) of patients diagnosed with invasive melanoma limited to the skin died within 10 years of diagnosis.⁹ Relapse of disease portends a poor prognosis. Long-term survival in patients, once distant metastatic melanoma develops, has been less than $10\%^{9,10}$ or around 22% at 5-years from diagnosis.⁸

A greater understanding of the role of tumor burden as a modulating factor in the efficacy of anti-melanoma therapy is important. It is apparent that treatments for melanoma have greater odds of efficacy in patients with a smaller, more-limited disease burden. This has been observed with regional therapies (talimogene laherparepvic, isolated limb infusion or perfusion), targeted therapies (dabrafenib + trametinib, vemurafenib) and with immunotherapies (pembrolizumab, ipilimumab, nivolumab). Specifically, for anti-PD-1 immunotherapy, it has been reported that the ratio of T-cell invigoration to tumor burden may be associated with anti-PD-1 response.^{11,12}

The introduction of therapies earlier in the course of the disease, when the tumor burden is much lower, to eradicate undetectable minimal residual disease prior to developing metastasis, therefore, has the potential for greatly increasing the chance of cure and substantially influencing melanomaspecific mortality. To extend the potential benefit of immunotherapy in the adjuvant setting to pediatric patients, pediatric patients diagnosed with Stage IIB/C melanoma ≥ 12 year old will also be included in this trial.

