5.4.1 Rationale for Treatment with Blinded Nivolumab

There is currently an unmet medical need for effective adjuvant therapies for patients diagnosed with Stage IIB and IIC cutaneous melanoma. Results from this study will help to define the role of nivolumab as an adjuvant immunotherapy in patients with Stage IIB and IIC cutaneous melanoma.

Cutaneous malignant melanomas are staged according to the AJCC (see Appendix 1 for List of Abbreviations) tumor/node/metastasis (TNM) classification and staging system. The AJCC 8th edition tumor staging for patients presenting with Stage II cutaneous malignant melanomas is shown below.⁶¹

| When T is | And N is | And M is | The pathological Stage is |
|--|----------|----------|---------------------------|
| T2b/T3a | NO | M0 | IIA |
| T3b/T4a | NO | M0 | IIB |
| T4b | NO | M0 | IIC |
| T2: >1.0–2.0 mm; T3: >2.0–4.0 mm; T4: >4.0 mm; a: without ulceration; b: with ulceration; N0: No regional metastases detected; M0: No evidence of distant metastasis | | | |

Stage IIB (T3b/T4a, N0, M0) and IIC (T4b, N0, M0) melanomas are classified as localized melanomas without nodal involvement but are a higher risk category compared to Stage I and IIA melanomas due to a relatively worse prognosis. Patients diagnosed with Stage IIB and IIC melanoma have 5-year melanoma-specific survival (MSS) reported as 87% and 82%, respectively. The corresponding 10-year survival rates have been reported as 82% and 75%, respectively. Initial relapses are reported most frequently as local/in-transit after resection of Stage IIB melanoma (47%), while systemic relapses are more frequent after resection of Stage IIC melanoma (52%).⁶¹

Lung is the most frequent site of systemic relapse reported for both subtypes, with the second most frequent site being the liver for patients diagnosed with Stage IIB and brain for patients diagnosed with Stage IIC melanoma.⁶² Once disease recurs, the site of initial relapse is the primary determinant of post-recurrence survival. Patients with systemic relapses have historically had a 5-year survival rate of 7% followed by 22, 33 and 57% for nodal, in-transit and local relapses respectively. ⁶³ These poor prognoses in patients with both systemic and local relapse highlight the importance of controlling localized disease to prevent melanoma metastases.⁶²

[figure not shown]

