7.2.1 Blinded Nivolumab or Placebo Treatment

After the participant's initial eligibility is established and informed consent has been obtained, the participant must be enrolled into the study through IRT website to obtain the participant number. Every participant who signs the informed consent form must be assigned a participant number in IRT. Specific instructions for using IRT will be provided to the investigational site in a separate document. The investigator or designee will register the participant for enrollment by following the enrollment procedures established by BMS. The following information is required for enrollment:

- Date that informed consent was obtained
- Date of birth (Year of birth, if local regulations do not allow use of entire date of birth)
- Gender at birth

Once enrolled in IRT, enrolled participants who have met all eligibility criteria will be ready to be randomized through the IRT. The sponsor, participants, investigator, and site staff will be blinded to the study drug administered during the study. Each investigative site must assign an unblinded pharmacist/designee, and an unblinded site monitor will be assigned by sponsor to provide oversight of drug supply and other unblinded study documentation. The randomization call may be performed by the blinded study coordinator or another suitable individual designated by the investigator; a notification of the actual treatment assignment will be sent by the IRT to the unblinded pharmacy site staff. The following information is required for participant randomization:

- Participant number
- Date of birth (Year of birth, if local regulations do not allow use of entire date of birth)
- Participants will be stratified by:
 - AJCC T-Stage, 8th edition (T3b vs. T4a vs. T4b)
- Participants will be treated with one of the following:

- Arm A: nivolumab 480 mg IV Q4W (for a maximum of 12 months from first dose of study treatment)

• Pediatric dosing as per Section 7.1.1

- Arm B: nivolumab matched placebo IV Q4W (for a maximum of 12 months from first dose of study treatment)

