10.3.1 Efficacy Analyses

10.3.1.1 Primary Endpoint Analysis

The primary endpoint is RFS. The primary endpoint of RFS will be programmatically determined based on the disease recurrence date provided by the investigator and is defined as the time between the date of randomization and the date of first recurrence (local, regional or distant metastasis), new primary melanoma (including melanoma in situ), or death (whatever the cause), whichever occurs first. For participants who remain alive and whose disease has not recurred or did not die, RFS will be censored on the date of last evaluable disease assessment. For those participants who remained alive and had no recorded post-randomization tumor assessment, RFS will be censored on the day of randomization. Censoring rules for the primary analysis of RFS are presented in Table 10.3.1.1-1.

| Situation | Date of Event or Censoring | Outcome |
|--|---|----------|
| Recurrence (local, regional, distant, new primary melanoma (including melanoma in situ)) | Date of first recurrence | Event |
| Death without recurrence | Date of death | Event |
| No baseline disease assessment | Date of randomization | Censored |
| No on-study disease assessments and no death | Date of randomization | Censored |
| No recurrence and no death | Date of last evaluable disease assessment | Censored |
| New anticancer therapy, tumor-directed radiotherapy, or tumor-directed surgery received without recurrence reported prior to or on the same day of disease assessment | Date of last evaluable disease assessment prior to or on the same date of initiation of subsequent therapy | Censored |
| Second non-melanoma primary cancer reported prior or on the same day of disease assessment | Date of last evaluable disease assessment prior to or on the same date of diagnosis of second non- melanoma primary cancer | Censored |

Table 10.3.1.1-1: Censoring Scheme for Primary Definition of RFS

RFS distributions will be compared between treatment groups (nivolumab vs placebo) using a twosided log-rank test stratified AJCC T-Stage at Screening at the overall significance level of 5% (two-sided) in all randomized participants.

The HR and corresponding 100x (1-adjusted α)% confidence intervals (CIs) will be estimated using a Cox proportional hazards model, with treatment group as a single covariate, stratified by the above factor.

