10.3.1.2 Secondary Endpoint Analyses

Overall Survival (OS)

OS is defined as the time between the date of randomization and the date of death. For participants without documentation of death, OS will be censored on the last date the participant was known to be alive. OS will be followed continuously while participants are on the study drug and every 12 weeks via in-person or phone contact after participants discontinue the study drug.

OS distributions will be compared in hierarchical testing order (order defined in Section 10.3.4) between treatment groups (nivolumab vs placebo) using a two-sided log-rank test stratified by AJCC T-Stage at Screening at the overall significance level of 5% (two-sided) in all randomized

participants. The hazard ratio and corresponding two-sided 100x (1-adjusted α)% CIs will be estimated using a Cox proportional hazards model, with treatment group as a single covariate, stratified by the above factors.

OS curves will be estimated using Kaplan-Meier (KM) product-limit methodology. Median OS with two-sided 95% CIs using the log-log transformation will be computed. In addition, OS rates at 6, 12, 18, 24, 30 and 36 months (and yearly after depending on follow-up) with two-sided 95% CIs using the log-log transformation will be computed.

Distant Metastasis-Free Survival (DMFS)

DMFS is defined as the time between the date of randomization and the date of first distant metastasis or date of death (whatever the cause), whichever occurs first.

Censoring rules for the analysis of DMFS are presented in Table 10.3.1.2-1.

Table 10.3.1.2-1:Censoring Scheme for Primary Definition of DMFS

| Situation | Date of Event or Censoring | Outcome |
|--|---|----------|
| Distant metastasis | Date of first distant metastasis | Event |
| Death without distant metastasis | Date of death | Event |
| No baseline disease assessment | Date of randomization | Censored |
| No on-study disease assessments and no death | Date of randomization | Censored |
| No distant metastasis and no death | Date of last evaluable disease assessment | Censored |

DMFS will be analyzed using similar analyses methods as for RFS. No multiplicity adjustment will be applied.

Investigator-Assessed Outcomes on Next-Line Therapies

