PFS2 is defined as the time from randomization to recurrence/objective disease progression after the start of the next-line of systemic anti-cancer therapy, or to the start of a second next-line systemic therapy, or to death from any cause, whichever occurs first.

In case PFS2 cannot be reliably determined, we will analyze the time from randomization to end or discontinuation of next-line treatment, second objective disease progression, or death from any cause, whichever occurs first.

The hazard ratio and corresponding 95% confidence intervals (CIs) will be estimated using a Cox proportional hazards model, with treatment group as a single covariate.

Objective response rates and duration of treatment on next-line therapies will be summarized.

[figure not shown]

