10.3.4 Interim Analyses

One formal interim analysis of RFS will be conducted when approximately 123 RFS events (80% information fraction) have been reached among all randomized participants. The stopping boundaries at the interim and final analyses will be derived based on the exact number of RFS events using Lan-DeMets alpha spending function with O'Brien-Fleming boundaries. With an interim RFS analysis at approximately 123 RFS events, the type I error would be 0.024 (two-sided). The type I error to be used for final RFS analysis would be 0.043 (two-sided).

RFS and OS will be tested using a hierarchical procedure: RFS will be compared first in all randomized participants with an alpha allocation of 0.05 (two-sided). If significant, OS will be compared in all randomized participants with an alpha allocation of 0.05 (two-sided).

One formal OS interim analysis will be conducted when approximately 166 deaths (60% information fraction) have been reached among all randomized participants, which is expected to occur after the final analysis of RFS.

It is estimated this would occur when all participants have a minimum follow-up of approximately 63 months from the randomization of the last participant. The estimated timing for this interim analysis is at 93 months. The stopping boundaries at the interim and final analyses will be derived based on the exact number of OS events using Lan-DeMets alpha spending function with O'Brien-Fleming boundaries. With an interim OS analysis at approximately 166 deaths, the type I error would be 0.008 (two-sided), the power 30.7%, and an observed HR of 0.644 or less would result in a statistically significant improvement. The type I error to be used for final OS analysis would be 0.048 (two-sided).

The DMC will have access to periodic unblinded interim reports of efficacy and safety to allow a risk/benefit assessment. Details will be included in the DMC charter.

The Statistical Analysis Plan will further describe the planned interim analyses.

11 **REFERENCES**

- ¹ Ossio R, Marin-Roldan R, Martinez-Said H, et al. Melanoma: a global perspective. Nature Reviews Cancer. 2017;17:393-394.
- ² Gershenwald J, Scolyer R, Hess K, et al. Melanoma Staging: Evidence-Based Changes in the American Joint Committee on Cancer Eighth Edition Cancer Staging Manual. CA Cancer J Clin. 2017;67(6):472–492.
- ³ BMS Internal Communication, data on file.

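### The PFS2 hazard ratio is the only time-to-event efficacy estimate left unstratified by T-stage: a small inconsistency that one phrase resolves

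*Combined protocol and SAP*

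**What the plan says.** Randomization has one stratification factor, given in Section 7.2.1 as "AJCC T-Stage, 8th edition (T3b vs. T4a vs. T4b").

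The time-to-event models are specified as follows:

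- **RFS (Section 10.3.1.1):** a Cox model "with treatment group as a single covariate, stratified by the above factor", the factor being T-stage at screening.
- **OS (Section 10.3.1.2):** a Cox model "with treatment group as a single covariate, stratified by the above factors", again T-stage.
- **DMFS (Section 10.3.1.2):** "DMFS will be analyzed using similar analyses methods as for RFS".
- **PFS2 and its fallback (Section 10.3.1.2, next-line therapies):** the HR and 95% interval "will be estimated using a Cox proportional hazards model, with treatment group as a single covariate". The sentence ends there.

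The PFS2 sentence is complete and the text on either side is intact, so the missing stratification is not a redaction. It follows the definition of the fallback endpoint, so it governs both.

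**The concern.** PFS2 and its fallback are both measured from randomization, as RFS, DMFS and OS are, so the design factor applies to them equally. The lack of a formal test does not explain the difference: DMFS is also outside the testing hierarchy, yet it follows the RFS methods.

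Hazard ratios are not collapsible. When a prognostic factor is left out of a Cox model, the treatment HR becomes an average over that factor and moves towards 1 even with perfect balance. PFS2 will be read beside RFS, DMFS and OS to judge whether early benefit persists through the next line of therapy. As written, that reading compares an averaged HR with within-T-stage HRs. The text also leaves room for an unplanned choice between two models that give slightly different numbers.

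No type I error is at stake. Section 10.3.4 states that "RFS and OS will be tested using a hierarchical procedure", and PFS2 is not part of that procedure.

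**Working it through.** The plan gives no event count, power or HR for PFS2, so there is no stated figure to reproduce. The question is how far the two models would differ.

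**Step 1. Prognostic strength of stage.** The protocol has no PFS2 rates by stage, so its other stage-specific risks serve as a range. Section 3.2 says that "approximately 25% of patients with Stage IIB disease and 40% of patients with Stage IIC disease will have a relapse" within 5 years, and gives 24-month relapse of 15% to 20% (IIB) and 30% (IIC). Section 5.4.1 gives "5-year melanoma-specific survival (MSS) reported as 87% and 82%, respectively", with 10-year survival of 82% and 75%. Under exponential hazards the IIC:IIB hazard ratio is ln(event-free proportion, IIC) / ln(event-free proportion, IIB):

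- 5-year relapse 25% vs 40%: ln(0.60)/ln(0.75) = 1.78
- 24-month relapse 20% vs 30%: ln(0.70)/ln(0.80) = 1.60
- 24-month relapse 15% vs 30%: ln(0.70)/ln(0.85) = 2.19
- 5-year melanoma-specific survival (MSS): ln(0.82)/ln(0.87) = 1.43
- 10-year MSS: ln(0.75)/ln(0.82) = 1.45

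**Step 2. Simulation.** Both Cox models were fitted to the same data in 6,000 simulated trials per scenario.

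- Assumed: n = 800 (the sample size is blacked out); stratum shares T3b 35%, T4a 25%, T4b 40%; exponential times; true within-stage HR 0.70; uniform censoring.
- Allocation was 2:1 in permuted blocks within the three strata. T3b and T4a carried the IIB risk and T4b the IIC risk.
- Censoring ran over 30 to 60 months or 63 to 93 months. The later window matches the minimum follow-up and timing given for the OS interim analysis in Section 10.3.4.

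Shift in HR = 0.70 × (ratio − 1), where ratio = unstratified HR / stratified HR:

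| Risks used | Ratio, 30–60 mo | Shift | Ratio, 63–93 mo | Shift |
|---|---|---|---|---|
| 5-year relapse 25/40 | 1.0036 | 0.00252 | 1.0058 | 0.00406 |
| 24-month relapse 20/30 | 1.0040 | 0.00280 | 1.0065 | 0.00455 |
| 24-month relapse 15/30 | 1.0101 | 0.00707 | 1.0160 | 0.01120 |
| 5-year MSS | 1.0007 | 0.00049 | 1.0010 | 0.00070 |
| 10-year MSS | 1.0005 | 0.00035 | 1.0008 | 0.00056 |

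The Monte Carlo standard error of each ratio is 0.0002 or less. With n = 600 and n = 1,000, run for the 25/40 and 15/30 scenarios only, the ratios run from 1.0033 to 1.0161.

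**Step 3. Differences within one trial.** At 30 to 60 months the two HRs differ by a median of 0.004 to 0.008, with a 95th percentile of 0.013 to 0.024.

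**Step 4. Precision and coverage.** The model standard error ratio, unstratified over stratified, is 0.9987 to 0.9996, so stratifying raises the standard error by about 0.1% at most (1/0.9987 = 1.0013). Coverage of the true within-stage HR is 95.3% to 95.9% unstratified and 95.1% to 95.6% stratified.

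**Step 5. Independent checks.**

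- A large-sample calculation in the same scenarios gives ratios of 1.0005 to 1.010 at 30 to 60 months and 1.0008 to 1.016 at 63 to 93 months.
- Solving the unstratified score equation with 4 to 8 years of follow-up and a IIB hazard of −ln(0.75)/5 per year gives limits of 0.701, 0.704 and 0.708 for stage hazard ratios of 1.4, 1.8 and 2.2.
- A separate simulation (1,500 trials, assumed n = 790, stage hazard ratio 1.8) gives mean standard errors of log HR of 0.1335 unstratified and 0.1336 stratified.

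**The case against.** The strongest reply is that nothing here is an error. The averaged HR is a valid estimand, its attenuation is conservative, its interval covers properly, and no test depends on it. In four of the five scenarios an HR of 0.70 still reads 0.70 to two decimals in both follow-up windows. With a standard error near 0.134, the 95% interval around 0.70 is exp(ln 0.70 ± 1.96 × 0.134), about 0.54 to 0.91, which dwarfs the shift. The largest values come from first-relapse risks, whereas PFS2 is a later event for which the MSS figures are arguably the closer proxy. All of this stands, and it is why the point ranks low.

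Three further points limit the claim without removing it:

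- Section 10.3 describes itself as a summary with a SAP to follow, and no separate SAP text was available, so the SAP may already stratify PFS2. The protocol wording would still differ between endpoints.
- That DMFS is stratified rests on its methods being described only as similar to those for RFS.
- Appendix 2 requires ethics and regulatory approval of amendments, and this change alone would not justify one. It can wait for the next amendment and be settled in the SAP meanwhile.

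A stated reason for leaving PFS2 unstratified would also remove the ambiguity, but the plan gives none, and no advantage of the unstratified model is apparent.

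**Conclusion.** The concern holds as a minor, optional improvement. On the protocol text, PFS2 and its fallback are the only time-to-event efficacy endpoints modelled without the randomization factor, and this is unexplained.

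At a true HR of 0.70 the unstratified HR lies nearer 1 by 0.05% to 1.0% at 30 to 60 months and by 0.1% to 1.6% at 63 to 93 months. The top value carries a 24-month hazard out to 93 months and should not be read as the expected effect. These sizes assume exponential hazards, the stated stratum shares and sample sizes, and relapse or MSS risks in place of PFS2 rates. Confidence is high for the wording and for the effect being small. What the eventual SAP specifies is not known.

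**What to change.** In the next-line-therapies part of Section 10.3.1.2, extend the Cox sentence so that the model is stratified by AJCC T-stage at screening, and state that this applies to both PFS2 and the end-of-next-line-treatment fallback. Use the same T-stage source as the RFS and OS models. Carry the wording into the PFS2 section of the SAP.

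The cost is one phrase, which can go into the next planned amendment. T-stage is already collected for randomization, the loss of precision is about 0.1% at most, and the sample size, event counts, power and alpha are unchanged.

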10.3.2 Safety Analyses

Safety and tolerability of nivolumab and placebo will be measured by the incidence of adverse events, serious adverse events, deaths, and laboratory abnormalities.

| Clinical Protocol | |
|-------------------|--|
| BMS-936558 | |

Safety analyses will be performed in all treated participants. Descriptive statistics of safety will be presented using NCI CTCAE v5 by treatment group (for the nivolumab and placebo arms). All onstudy AEs, treatment-related AEs, SAEs, and treatment-related SAEs will be tabulated using worst grade per NCI CTCAE v5 criteria by system organ class and preferred term. On-study lab parameters including hematology, chemistry, liver function, and renal function will be summarized using worst grade NCI CTCAE v5 criteria.

10.3.3 Other Analyses

10.3.3.3 Pharmacokinetic Analyses

The nivolumab concentration data obtained in this study will be combined with data from other studies in the clinical development program to develop a population PK model. This model will

be used to evaluate the effects of intrinsic and extrinsic covariates on the PK of nivolumab. In addition, exposure-response analyses with selected efficacy and safety endpoints may be conducted. Results of population PK and exposure response-analyses will be reported separately.

